## **11.4 Review of cumulative safety data**

Routine safety review occurs at the start of enrollment and then throughout the study.

Reviews proceed from a standardized set of protocol-specific safety data reports. These reports are produced by the SDMC and include queries to the HVTN CRSs. Events are tracked by internal reports until resolution.

### **11.4.1 Daily review**

Daily safety reviews are routinely conducted by HVTN Core for events requiring expedited reporting to DAIDS, and events that meet safety pause criteria or prompt HVTN 121 PSRT AE review criteria.

### **11.4.2 Weekly review**

During the injection phase of the trial, the HVTN 121 PSRT reviews clinical safety reports on a weekly basis and conducts calls to review the data as appropriate. After the injections and the final 2-week safety visits are completed, less frequent reporting and safety reviews may be conducted at the discretion of the HVTN 121 PSRT. HVTN Core reviews reports of clinical and laboratory AEs. Events identified during the review that are considered questionable, inconsistent, or unexplained are referred to the HVTN CRS clinic coordinator for verification.

## **11.5 Study termination**

This study may be terminated early by the determination of the HVTN 121 PSRT, a pertinent national regulatory authority, NIH, Office for Human Research Protections (OHRP), the FDA, or study product developer. In addition, the

conduct of this study at an individual HVTN CRS may be terminated by the determination of the IRB/EC and any applicable RE.

## 12 Protocol conduct

This protocol and all actions and activities connected with it will be conducted in compliance with the principles of GCP (ICH6), and according to DAIDS and HVTN policies and procedures as specified in the *HVTN Manual of Operations*, DAIDS Clinical Research Policies and Standard Procedures Documents including procedures for the following:

- Protocol registration, activation, and implementation;
- Informed consent, screening, and enrollment;
- Study participant reimbursement;
- Clinical and safety assessments;
- Safety monitoring and reporting;
- Data collection, documentation, transfer, and storage;
- Participant confidentiality;
- Study follow-up and close-out;
- Quality control;
- Protocol monitoring and compliance;
- Advocacy and assistance to participants regarding negative social impacts associated with the vaccine trial;
- Risk reduction counseling;
- Specimen collection, processing, and analysis;
- Exploratory and ancillary studies and sub-studies, and
- Destruction of specimens.

Any policies or procedures that vary from DAIDS and HVTN standards or require additional instructions (eg, instructions for randomization specific to this study) will be described in the HVTN 121 *Study Specific Procedures*.

## **12.1 Social impacts**

Participants in this study risk experiencing discrimination or other personal problems, resulting from the study participation itself or from the development of VISP. The HVTN CRS is obliged to provide advocacy for and assistance to participants regarding these negative social impacts associated with the vaccine trial. If HVTN CRS staff have questions regarding ways to assist a participant dealing with a social impact, a designated NIAID or HVTN Core representative can be contacted.

Social harms are tabulated by the SDMC and are subjected to descriptive analysis. The goal is to reduce their incidence and enhance the ability of study staff to mitigate them when possible.

Summary tables of social impact events will be generated weekly, and made available for review by the protocol chairs, protocol team leader, and the designated NIAID representative.

## **12.2 Emergency communication with study participants**

As in all clinical research, this study may generate a need to reach participants quickly to avoid imminent harm, or to report study findings that may otherwise concern their health or welfare.

When such communication is needed, the CRS will request that its IRB/EC and any applicable RE expedite review of the message. If this review cannot be completed in a timeframe consistent with the urgency of the required communication, the site can contact the participant without IRB/EC approval if such communication is necessary to avoid imminent harm to the study participant. The CRS must notify the IRB/EC and any applicable RE of the matter as soon as possible.

## 13 Version history

The Protocol Team may modify the original version of the protocol. Modifications are made to HVTN protocols via clarification memos, letters of amendment, or full protocol amendments.

The version history of, and modifications to, Protocol HVTN 121 are described below.

### Protocol history and modifications

#### **Date: September 12, 2018**

---

*Protocol version: 1.02*

*Protocol modification: Full Protocol Amendment 1*

- Item 1 Added to the protocol cover page, IND number 018361
- Item 2 Revised in Section 9.2, *Pre-enrollment procedures*, the eligibility assessment period from 30 to 28 days to harmonize with Section 7, *Selection and withdrawal of participants*, last paragraph
- Item 3 Revised in Section 9.3, *Enrollment and vaccination visit*, SLE assessment and urinalysis
- Item 4 Revised in Section 9.4, *Follow-up visits*, Appendix D, *Table of procedures (for sample informed consent form)*, and Appendix F, *Procedures at HVTN CRS*, the timing of when SLE assessments done at some scheduled follow-up visits
- Item 5 Added in 11.2.2, *AE reporting*, new guidance to address SLE flare
- Item 6 Revised Table 11-1 (now Table 11-8), *AE notification and safety pause/AE review rules*, a new pause rule
- Item 7 Updated in Section 13, Version history
- Item 8 Corrected cross-referencing errors and updated document URLs

#### **Date: July 12, 2018**

---

*Protocol version: 1.0*

*Protocol modification:*

Original protocol

## 14 Document references (other than literature citations)

Other documents referred to in this protocol, and containing information relevant to the conduct of this study, include:

- Assessment of Understanding. Accessible through the HVTN protocol-specific website.
- Current CDC Guidelines.
- Revised Recommendations for HIV Testing of Adults, Adolescents, and Pregnant Women in Health-Care Settings. Available at <http://www.cdc.gov/mmwr/PDF/rr/rr5514.pdf>
- Revised Guidelines for HIV Counseling, Testing, and Referral. Available at <http://www.cdc.gov/mmwr/preview/mmwrhtml/rr5019a1.htm>
- DAIDS Clinical Research Policies and Standard Procedures Documents. Available at <https://www.niaid.nih.gov/research/daids-clinical-research-policies-standard-procedures>
- DAIDS Protocol Registration Manual. Available at <https://www.niaid.nih.gov/sites/default/files/prmanual.pdf>
- DAIDS Table for Grading the Severity of Adult and Pediatric Adverse Events. Corrected Version 2.1, July 2017. Available at <http://rsc.tech-res.com/clinical-research-sites/safety-reporting/daids-grading-tables>
- The Manual for Expedited Reporting of Adverse Events to DAIDS. Version 2.0, January 2010. Available at <http://rsc.tech-res.com/clinical-research-sites/safety-reporting/manual>
- HVTN Certificate of Confidentiality. Accessible through the HVTN website.
- HVTN 121 Special Instructions. Accessible through the HVTN protocol-specific website.
- HVTN 121 Study Specific Procedures. Accessible through the HVTN protocol-specific website.
- HVTN 121 Site Lab Instructions. Accessible through the HVTN protocol-specific website.
- HVTN Manual of Operations. Accessible through the HVTN website.

- Dangerous Goods Regulations (updated annually), International Air Transport Association. Available for purchase at <http://www.iata.org/publications/dgr/Pages/index.aspx>.
- Lab assay algorithm (available upon request)
- International Conference on Harmonisation (ICH) E6, Guideline for Good Clinical Practice: Section 4.8, Informed consent of trial subjects. Available at <http://www.ich.org/products/guidelines/efficacy/article/efficacy-guidelines.html>
- Participants' Bill of Rights and Responsibilities. Accessible through the HVTN website.
- NIH *Guidelines for Research Involving Recombinant or Synthetic Nucleic Acid Molecules*. Available at <http://osp.od.nih.gov/office-biotechnology-activities/biosafety/nih-guidelines>
- NIH Policy on Reporting Race and Ethnicity Data: Subjects in Clinical Research. Available at <http://grants1.nih.gov/grants/guide/notice-files/NOT-OD-01-053.html>
- Pharmacy Guidelines and Instructions for DAIDS Clinical Trials Networks, July 2008.
- Requirements for Source Documentation in DAIDS Funded and/or Sponsored Clinical Trials. Available at <https://www.niaid.nih.gov/sites/default/files/daids-sourcedocpolicy.pdf>
- Title 21, CFR, Part 50. Available at <http://www.accessdata.fda.gov/scripts/cdrh/cfdocs/cfcfr/CFRSearch.cfm?CFRPart=50>
- Title 45, CFR, Part 46. Available at <https://www.hhs.gov/ohrp/regulations-and-policy/regulations/45-cfr-46/index.html>

See Section 16 for literature cited in the background and statistics sections of this protocol.

## 15 Acronyms and abbreviations

ADCC	antibody-dependent cellular cytotoxicity
AE	adverse event
ALT	alanine amino transferase
APS or APLS syndrome	antiphospholipid syndrome or antiphospholipid antibody syndrome
ART	antiretroviral therapy
ASIA	autoimmune / inflammatory syndrome induced by adjuvants
AST	aspartate aminotransferase
AUC-MB	area-under-the-magnitude-breadth curve
β-HCG	beta human chorionic gonadotropin
BAMA	binding antibody multiplex assay
bnAb	broadly neutralizing antibody
CAB	Community Advisory Board
CBC	complete blood count
CDC	US Centers for Disease Control and Prevention
cDNA	complementary DNA
CFR	Code of Federal Regulations
CHAVI	Center for HIV-AIDS Vaccine Immunology
CHO cell	Chinese hamster ovary cell
CIOMS	Council for International Organizations of Medical Sciences
CNS	central nervous system
CRF	case report form
CRPMC	Clinical Research Products Management Center
CRS	clinical research site
DAERS	DAIDS Adverse Experience Reporting System
DAIDS	Division of AIDS
DHHS	US Department of Health and Human Services
dsDNA	double-strand DNA
EAE	adverse events requiring expedited reporting to DAIDS
EC	Ethics Committee
EIA	enzyme immunoassay
ELISA	enzyme-linked immunosorbent assay
FDA	US Food and Drug Administration
FHCRC	Fred Hutchinson Cancer Research Center
GCP	Good Clinical Practice
GMT	geometric mean titer
GSID	Global Solutions for Infectious Diseases

GTL	GranToxiLux
HBsAg	hepatitis B surface antigen
HCDR3	heavy chain complementarity determining region 3
HCV	hepatitis C virus
HIPAA	Health Insurance Portability and Accountability Act
HIV	human immunodeficiency virus
HLA	human leukocyte antigen
HVTN	HIV Vaccine Trials Network
IB	Investigator's Brochure
ICF	informed consent form
ICH	International Conference on Harmonisation
ICS	intracellular cytokine staining
IFN- $\gamma$	interferon gamma
IL	interleukin
IM	intramuscular
IND	Investigational New Drug
IRB	Institutional Review Board
IUD	intrauterine device
mAbs	monoclonal antibodies
MedDRA	Medical Dictionary for Regulatory Activities
MMR	measles, mumps, and rubella
nAb	neutralizing antibody
NAEPP	National Asthma Education and Prevention Program
NGS	next generation sequencing
NIAID	National Institute of Allergy and Infectious Diseases
NIH	US National Institutes of Health (US NIH)
OHRP	US Office for Human Research Protections
OPV	oral polio vaccine
PAB	Pharmaceutical Affairs Branch
PBMC	peripheral blood mononuclear cell
PCA	principal component analysis
PCR	polymerase chain reaction
PSRT	Protocol Safety Review Team
pTfh	peripheral follicular helper T
qPCR	quantitative polymerase chain reaction
RAB	Regulatory Affairs Branch
RAPID3	Routine Assessment of Patient Index Data 3
RE	regulatory entity
RSC	Regulatory Support Center

SAE	serious adverse event
SCHARP	Statistical Center for HIV/AIDS Research and Prevention
SDMC	statistical and data management center
SELENA Assessment	Safety of Estrogens in Lupus Erythematosus National
SICF	sample informed consent form
SLE	systemic lupus erythematosus
SLEDAI	SLE Disease Activity Index
SLICC/ACR DI	Systemic Lupus International Collaborating Clinics/American College of Rheumatology Damage Index
SMB	Safety Monitoring Board
SPT	DAIDS Safety and Pharmacovigilance Team
SSA	Sjögren's syndrome A
TB	tuberculosis
Tfh	T follicular helper
TNF- $\alpha$	tumor necrosis factor alpha
Treg	T regulatory
UW-VSL	University of Washington Virology Specialty Laboratory
VISP	Vaccine induced seropositivity
WBC	white blood cells

## Appendix E Laboratory procedures

Procedure	Ship to 	Assay Location 	Tube 	Tube size (vol. capacity) 	Tube volume (mL)														Total	
					1	2	3	4	5	6	7	8	9	10	11	12 	13	14		
					Screening	D0	D7	D14	D28	D35	D42	D84	D168	D175	D182	D210	D238	D364		
Month:	visit 	M0	M0.25	M0.5	M1	M1.25	M1.5	M3	M6	M6.25	M6.5	M7.5	M8.5	M12						
					AIDSVAX B/E				AIDSVAX B/E				AIDSVAX B/E							
BLOOD COLLECTION																				
Screening or diagnostic assays																				
Screening HIV test	Local Lab	Local Lab	SST	5mL	5	—	—	—	—	—	—	—	—	—	—	—	—	—	5	
HBsAg/anti-HCV	Local Lab	Local Lab	SST	5mL	5	—	—	—	—	—	—	—	—	—	—	—	—	—	5	
Syphilis	Local Lab	Local Lab	SST	5mL	5	—	—	—	—	—	—	—	—	—	—	—	—	—	5	
HIV diagnostics 	UW-VSL	UW-VSL	EDTA	10mL	—	—	—	—	—	—	10	—	—	10	—	—	—	20 	40	
Safety labs																				
Hb A1C	Local lab	Local lab	EDTA	5mL	5	—	—	—	—	—	—	—	—	—	—	—	—	—	5	
CBC/ Diff/ platelets	Local lab	Local lab	EDTA	5mL	5	5	5	5	5	5	5	5	5	5	5	5	5	5	60	
Chemistry panel 	Local lab	Local lab	SST	5mL	5	—	—	5	—	—	5	5	—	—	5	—	5	—	30	
Complement profile C3/C4/CH50	Local lab	Local lab	SST	5mL	5	5	5	5	5	5	5	5	5	5	5	5	5	5	60	
Anti-dsDNA	Local lab	Local lab	SST	5mL	5	5	5	5	5	5	5	5	5	5	5	5	5	5	60	
Immunogenicity assays																				
Host genetics 	CSR	HVTN Labs	ACD	8.5mL	—	17	—	—	—	—	—	—	—	—	—	—	—	—	17	
Cellular assays																				
ICS	CSR	HVTN Labs	ACD	8.5mL	—	25.5	—	—	—	—	—	—	—	—	25.5	—	—	—	25.5	76.5
T and B cell phenotyping	CSR	HVTN Labs	ACD	8.5mL	—	34	—	—	—	42.5	17	—	42.5	42.5	34	—	—	34	246.5	
Memory B cell sorts and recombinant Ab production	CSR	Non-HVTN Labs at Duke-DHVI	ACD	8.5mL	—	—	—	—	—	—	25.5	—	—	—	25.5	—	—	51	102	
Plasma cell sorts for B cell repertoire analysis	CSR	Non-HVTN Labs at Duke-DHVI	ACD	8.5mL	—	—	—	—	—	—	—	—	—	—	25.5	—	—	—	25.5	
Humoral assays																				
Binding Ab	CSR	HVTN Labs	SST	8.5mL	—	8.5	—	—	—	—	8.5	—	8.5	—	8.5	—	—	8.5	42.5	
Neutralizing Ab	CSR	HVTN Labs	SST	8.5mL	—	8.5	—	—	—	—	8.5	—	8.5	—	8.5	—	—	8.5	42.5	
ADCC	CSR	HVTN Labs	SST	8.5mL	—	y	—	—	—	—	y	—	y	—	y	—	—	y	0	
bnAb epitope binding and blocking assays	CSR	Non-HVTN Labs at Duke-DHVI	ACD	8.5mL	—	z	—	—	—	—	z	z	—	z	z	z	—	—	z	0
Innate immunity																				
Serum cytokines	CSR	HVTN Labs	SST	5mL	—	5	—	—	—	5	5	—	5	5	5	—	—	5	35	
Sequencing																				
Next generation sequencing for VH and VL	CSR	Non-HVTN Labs at Duke-DHVI	ACD	8.5mL	—	25.5	—	—	—	—	25.5	—	—	25.5	25.5	—	—	25.5	127.5	
RNAseq of Tfh and B cell populations	CSR	Non-HVTN Labs at Duke-DHVI	ACD	8.5mL	—	25.5	—	—	—	—	25.5	—	—	25.5	25.5	—	—	25.5	127.5	
Specimen storage																				
PBMC	CSR		ACD	8.5mL	127.5	17	—	—	—	—	—	—	17	42.5	17	—	—	85	306	
Plasma	CSR		ACD	8.5mL	z	z	—	—	—	z	z	—	z	z	z	—	—	z	0	
Serum	CSR		SST	8.5mL	17	—	—	—	—	—	—	—	—	—	—	—	—	8.5	25.5	
Visit total					185	182	15	20	15	63	146	20	97	182	205	0	20	297	1444	
56-Day total					185	366	381	401	416	479	480	243	97	278	483	483	225	297		
URINE COLLECTION																				
Urinalysis with microscopy 	Local lab	Local lab			X	X	X	X	X	X	X	X	X	X	X	—	X	—		
Spot urine protein:creatinine ratio	Local lab	Local lab			X	X	X	X	X	X	X	X	X	X	X	—	X	—		
Pregnancy test 	Local lab	Local lab			X	X	—	—	X	—	—	—	X	—	—	—	—	—		

 CSR = Central Specimen Repository; UW-VSL = University of Washington Virology Specialty Laboratory (Seattle, Washington, USA).

 HVTN Laboratories include FHCRC = Fred Hutchinson Cancer Research Center (Seattle, Washington, USA); Duke = Duke University Medical Center (Durham, North Carolina, USA).

Non-HVTN laboratory: Duke Human Vaccine Institute (Durham, North Carolina, USA).

 Screening may occur over the course of several contacts/visits up to and including before vaccination on day 0. Storage specimens should be drawn no later than Day -15.

 Local labs may assign appropriate alternative tube types for locally performed tests.

 Chemistry panels are defined in Section 9.2 (pre-enrollment) and Section 9.4 (Follow-up visits).

 Immunogenicity assays will be performed at M0, M1.25, M1.5, M6.25, and M6.5. Based on the number of responders observed at these timepoints, lab assays may be performed on participants for humoral and cellular responses at other timepoints.

 Genotyping may be performed on enrolled participants using cryopreserved PBMC collected at baseline, initially in participants who demonstrate vaccine-induced T-cell responses at postvaccination timepoints.

 For a participant who was born female (ie, assigned female sex at birth), pregnancy test must be performed on urine or blood specimens within 24 hours of vaccination with negative results received prior to vaccination. Persons who have undergone total hysterectomy or bilateral oophorectomy (verified by medical records), are not required to undergo pregnancy testing.

 At an early termination visit for a withdrawn or terminated participant who is not HIV-infected (see Section 9.10), blood should be drawn for HIV diagnostic testing, as shown for visit 14 above. If a participant has a confirmed diagnosis of HIV infection, do not collect blood for HIV diagnostic testing (see Section 9.12).

 Urinalysis with microscopy is defined in Sections 7.1, 9.2, and 9.7.

 For information concerning the visit 12 health assessment contact, see Section 9.4 and HVTN 121 SSP.

 For participants with confirmed diagnosis of HIV infection, only specimens required for protocol-specified safety laboratory tests, urinalysis, spot urine protein:creatinine ratio, and pregnancy tests will be collected.

y = SST collected for binding Ab and neutralizing Ab assays will also cover specimen needs for ADCC; no separate blood draw is needed.

z = Up to 10 x 1mL aliquots of ACD plasma will be harvested during PBMC processing; no separate blood draw is needed.

## Appendix F Procedures at HVTN CRS

Visit:	01 	02	03	04	05	06	07	08	09	10	11	12	13	14
Day:		D0	D7	D14	D28	D35	D42	D84	D168	D175	D182	D210	D238	D364
Month:		M0	M0.25	M0.5	M1	M1.25	M1.5	M3	M6	M6.25	M6.5	M7.5	M8.5	M12
Procedure	Scr.	VAC1			VAC2				VAC3					
Study procedures														
Signed screening consent (if used)	X	—	—	—	—	—	—	—	—	—	—	—	—	—
Assessment of understanding	X	—	—	—	—	—	—	—	—	—	—	—	—	—
Signed protocol consent	X	—	—	—	—	—	—	—	—	—	—	—	—	—
Medical history	X	—	—	—	—	—	—	—	—	—	—	—	—	—
Complete physical exam	X	X	X	X	X	X	X	X	X	X	X	—	X	X
Risk reduction counseling 	X	X	X	X	X	X	X	X	X	X	X	—	X	X
Pregnancy prevention assessment 	X	X	X	X	X	X	X	X	X	X	X	—	X	X
Behavioral risk assessment 	X	—	—	—	—	—	—	X	X	—	—	—	X	X
Confirm eligibility, obtain demographics	X	—	—	—	—	—	—	—	—	—	—	—	—	—
Social impact assessment	—	X	X	X	X	X	X	X	X	X	X	—	X	X
Social impact assessment questionnaire	—	—	—	—	—	—	—	X	X	—	—	—	—	X
Concomitant medications	X	X	X	X	X	X	X	X	X	X	X	—	X	X
Intercurrent illness/adverse experience	—	X	X	X	X	X	X	X	X	X	X	—	X	X
HIV infection assessment 	X	—	—	—	—	—	X	—	—	—	X	—	—	X
Confirm HIV test results provided to participant	—	X	—	—	—	—	—	X	—	—	—	—	X	—
SLE status assessment/functional assessment 	X	X	X	X	X	X	X	X	X	X	X	—	X	—
Health assessment contact 	—	—	—	—	—	—	—	—	—	—	—	X	—	—
Local lab assessment														
Urinalysis and spot urine protein;creatinine ratio	X	X	X	X	X	X	X	X	X	X	X	—	X	—

HVTN 121 Version 2.0 / September 14, 2018

Visit:	01 	02	03	04	05	06	07	08	09	10	11	12	13	14
Day:		D0	D7	D14	D28	D35	D42	D84	D168	D175	D182	D210	D238	D364
Month:		M0	M0.25	M0.5	M1	M1.25	M1.5	M3	M6	M6.25	M6.5	M7.5	M8.5	M12
Procedure	Scr.	VAC1			VAC2				VAC3					
Pregnancy (urine or serum HCG) 	X	X	—	—	X	—	—	—	X	—	—	—	—	—
CBC, differential/platelets	X	X	X	X	X	X	X	X	X	X	X	—	X	—
Chemistry panel (see Section 9.2)	X	—	—	X	—	—	X	X	—	—	X	—	X	—
Syphilis, Hepatitis B, Hepatitis C	X	—	—	—	—	—	—	—	—	—	—	—	—	—
Complement profile (C3/C4/CH50)	X	X	X	X	X	X	X	X	X	X	X	—	X	—
Anti-dsDNA	X	X	X	X	X	X	X	X	X	X	X	—	X	—
Vaccination procedures														
Vaccination 	—	X	—	—	X	—	—	—	X	—	—	—	—	—
Reactogenicity assessments 	—	X	—	—	X	—	—	—	X	—	—	—	—	—

 Enrollment and screening visits can occur on the same day

 For specimen collection requirements, see [Appendix E](#).

 Includes transmission risk reduction counseling for HIV-infected participants.

 Pregnancy prevention assessment is required only for participants who were assigned female sex at birth and are capable of becoming pregnant.

 Not applicable to HIV-infected participants.

 Includes pre-test counseling and HIV testing. A subsequent follow-up contact is conducted to provide post-test counseling and to report results to participant. If a participant has a confirmed diagnosis of HIV infection, do not perform HIV infection assessment.

 SELENA-SLEDAI, RAPID3. SLICC/ACR at screening only.

 CRS staff and study participants will be in contact to collect information about their health (see HVTN 121 SSP).

 For participants with a confirmed diagnosis of HIV infection, only specimens listed under “Safety labs,” urinalysis, spot urine protein:creatinine ratio, and pregnancy tests specified in [Appendix E](#) will be collected.

 For a participant who was assigned female sex at birth, pregnancy test must be performed on the day of vaccination prior to vaccination. Pregnancy test to determine initial eligibility may be performed at screening, but must also be done on day 0 prior to first vaccination. Persons who are NOT of reproductive potential due to having undergone total hysterectomy or bilateral oophorectomy (verified by medical records), are not required to undergo pregnancy testing. Serum pregnancy tests may be used to confirm the results of, or substitute for, a urine pregnancy test, in accordance with local regulatory requirements.

[figure not shown]
 Not applicable to HIV-infected participants.

 Blood draws required at vaccination visits must be performed prior to administration of study product; however, it is not necessary to have results prior to administration, except for results of a serum pregnancy test, if indicated. Lab tests may be drawn within the 3 days prior to vaccination.

 Reactogenicity assessments performed daily for at least 7 days postvaccination (see Section 9.8)

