### 10.2 Total blood volume

Required blood volumes per visit are shown in [Appendix E](#). Not shown is any additional blood volume that would be required if a safety lab needs to be repeated, or if a serum pregnancy test needs to be performed. The additional blood volume would likely be minimal. The total blood volume drawn for each participant will not exceed 500 mL in any 56-day (8-week) period.

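### The 500 mL per 56-day blood limit is met at Day 42 only if the 144.5 mL screening storage draw has left the window, yet Appendix F allows same-day screening and enrollment without excepting that draw

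*Combined protocol and SAP*

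**What the plan says.** Section 10.2 sets the limit: "The total blood volume drawn for each participant will not exceed 500 mL in any 56-day (8-week) period". It adds that repeat safety labs and serum pregnancy tests are not in the table.

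The Appendix E screening column includes stored PBMC and serum. The PBMC storage row starts "8.5mL 127.5 17", meaning 127.5 mL at screening and 17 mL at Day 0. The serum storage row has 17 mL at screening. Footnote 3 says "Screening may occur over the course of several contacts/visits up to and including before vaccination on day 0", and then "Storage specimens should be drawn no later than Day -15".

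The printed visit totals from screening to Day 42 are "185 182 15 20 15 63 146" mL. The printed 56-day totals from screening to Day 84 are "185 366 381 401 416 479 480 243" mL.

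Appendix F footnote 1 says "Enrollment and screening visits can occur on the same day". Footnote 2 opens "For specimen collection requirements, see" and points to Appendix E. Section 9.9 leaves visit windows to the Study Specific Procedures.

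**The concern.** The three statements do not fit together. The cap is unconditional. The timing that keeps the schedule under the cap is worded as *should*, with no reason given and no mention of 500 mL. A footnote in the other appendix allows a single-day visit that cannot meet that timing.

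The printed 56-day row shows the dependence. It moves from 479 mL at Day 35 to 480 mL at Day 42, although the Day 42 visit itself takes 146 mL. A rise of 1 mL is possible only if about 145 mL drops out of the window at the same moment.

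What is at stake is a stated participant-protection limit; Section 2.1 lists respect for blood-draw limits among the ways risk is minimized. A site that discovers the problem at Day 42 would have to exceed the cap or give up samples taken two weeks after the second vaccination. Those samples feed secondary endpoints 2, 4 and 5 in a trial of 16 participants.

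**Working it through.** **Inputs, re-added from the Appendix E rows (mL)**

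- Screening labs: eight 5 mL tubes = 40
- Screening storage: 127.5 + 17 = 144.5
- Screening total: 40 + 144.5 = 184.5 (printed 185)
- Day 0: 181.5 (printed 182)
- Day 7: 15; Day 14: 20; Day 28: 15
- Day 35: 62.5 (printed 63)
- Day 42: 145.5 (printed 146)

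**Counting rule used by the table.** Draws exactly 56 days old are counted:

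- Day 84 = Day 28 + Day 35 + Day 42 + Day 84 = 15 + 62.5 + 145.5 + 20 = 243, as printed.
- Day 238 = Day 182 + Day 238 = 205 + 20 = 225, as printed.

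**Reproducing the plan's figures**

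- Day 35 with all screening blood: 184.5 + 181.5 + 15 + 20 + 15 + 62.5 = 478.5 (printed 479).
- Day 0 to Day 42 alone: 181.5 + 15 + 20 + 15 + 62.5 + 145.5 = 439.5.
- Day 42 with the 40 mL of labs but without storage: 439.5 + 40 = 479.5 (printed 480).

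So the printed Day 42 figure keeps the eligibility labs in the window and leaves the storage draw out.

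**With storage in the window**

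- Full screening column: 439.5 + 184.5 = 624; 624 − 500 = 124 over.
- Storage counted but the eligibility labs already out: 439.5 + 144.5 = 584; 584 − 500 = 84 over.

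**When storage is in the window.** Under the table's rule, storage is out only if it precedes the Day 42 visit by at least 57 days. The totals below keep the 40 mL of labs in the window.

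| Storage draw | Day 42 visit held on | Gap (days) | Total, table's rule | Total, 56 calendar days counted inclusively |
|---|---|---|---|---|
| Day -28 | Day 42 | 70 | 479.5 | 479.5 |
| Day -15 | Day 42 | 57 | 479.5 | 479.5 |
| Day -15 | Day 41 | 56 | 624 | 479.5 |
| Day -15 | Day 40 | 55 | 624 | 624 |
| Day -14 | Day 42 | 56 | 624 | 479.5 |
| Day -13 | Day 42 | 55 | 624 | 624 |
| Day 0 | Day 42 | 42 | 624 | 624 |

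At the Day -15 limit the slack is nil under the table's rule and one day under inclusive counting. A Day -28 draw leaves 70 − 57 = 13 days under the table's rule.

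**The case against.** The strongest reply is that the plan already handles this. Appendix F footnote 2 follows directly on footnote 1 and sends the reader to Appendix E. There, footnote 3 puts the general permission to screen up to Day 0 next to a specific limit for storage specimens, and a specific rule normally qualifies a general one. Screening may span several contacts, so a site can draw storage early and finish eligibility on Day 0. The schedule also seems to expect an earlier contact: Appendix F marks confirmation of HIV results at Day 0, and Section 9.3 ties this to a previous visit. A site reaching 624 mL by same-day screening would have to overlook both footnote 3 and the cap.

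Most of that stands, and it lowers the severity. It does not remove the conflict. Footnote 1 read literally permits a visit that cannot meet Day -15, and footnote 3 is advisory and does not say that the cap depends on it.

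A reader might infer three stronger things:

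- **The table is miscalculated.** It is not. Every 56-day total reproduces to rounding under the table's own rule.
- **The cap holds only if storage is drawn by Day -15 and Day 42 is never early.** This is too strong. Day -15 is the latest date, and an earlier draw leaves room for an early visit. Whether an early Day 42 visit is allowed cannot be checked without the Study Specific Procedures.
- **The extra blood loss would lower hemoglobin and be mistaken for a vaccine or disease effect.** Participants assigned female at birth may enter at 11.0 g/dL, and hemoglobin is a primary safety measure. But the documents give no figure to support the step from draw volume to a misread result.

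**Conclusion.** The point holds as a consistency defect. Compliance with Section 10.2 at Day 42 depends on when the 144.5 mL storage draw is taken, and Appendix F footnote 1 does not protect that timing. Same-day screening and enrollment with the full screening column gives 624 mL, 124 mL (24.8%) over the cap, under either way of counting. Storage drawn between Day -14 and Day 0 gives 584 to 624 mL under the table's rule; under inclusive counting the problem starts at Day -13.

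The early-visit route to a breach is conditional. It matters for a storage draw at or near Day -15 and rests on windows not given here.

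The primary neutralizing antibody endpoint is not directly exposed: its post-vaccination sample is at Day 182, where the printed 56-day total is 483 mL and no screening blood is in the window. Severity is should-fix.

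**What to change.** Reconcile Appendix F footnote 1, Appendix E footnote 3 and Section 10.2 so that every permitted timing of the storage draw is consistent with the cap, and cross-refer the two footnotes to each other and to Section 10.2. Recheck the 56-day row at the earliest visit dates that the Study Specific Procedures permit, and state the counting rule used. Which rule to adopt for the storage draw is for the sponsor to decide.

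The cost is a few footnote edits and one rechecked table row. Depending on the rule chosen, some participants might enroll a little later or give less pre-vaccination storage blood. The baseline neutralizing and binding antibody samples are drawn at Day 0 and are unaffected.
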